6.3.1.2 Body Surface Area Affected

The assessment of the %BSA affected is an estimate of the percentage of total involved skin with AD. For the purpose of clinical estimation, the total palmar surface of the subject's palm and digits may be assumed to be approximately equivalent to 1% BSA. The %BSA affected by AD will be evaluated from 0% to approximately 100% (scalp excluded). Details on calculation of approximate %BSA involvement in each subject are provided in [Appendix 6](#). Percentage BSA is a static assessment made without reference to previous scores.

6.3.1.3 Eczema Area and Severity Index

The EASI will be assessed at every clinic visit. It quantifies the severity of a subject's AD based on both lesion severity and the %BSA affected [[Hanifin](#), 2001]. The subject's scalp is excluded from this assessment. The EASI is a composite score ranging from 0 to 72 that takes into account the degree of erythema, edema/papulation, excoriation, and lichenification (each scored from 0 to 3 separately) for each of four body

regions, with adjustment for the %BSA involved for each body region relative to the whole body. A detailed procedure of EASI score calculation is provided in [Appendix 6](#). The EASI score will be calculated in the CRF based on the subject's age, the rating scores for each region, and the number of handprints involved for each region.

6.3.2 Assessments Completed by Subject or Caregiver

A summary table of assessments completed by subject or caregiver, broken down by age group, is provided in [Appendix 7](#).

6.3.2.3 Peak Pruritus-Numeric Rating Scale

The PP-NRS is a scale used to quickly assess itch/pruritus severity over a 24-hour period. The subject or caregiver will utilize the scale to assess peak pruritus QD and record the results in their daily diaries. The itch

rating can be done before or after study drug administration since it should reflect the past 24 hours. On clinic visit days, the PP-NRS will be assessed in the clinic. PP-NRS should be completed every day, even if subjects are not actively applying study drug. For subjects ages 2 to < 12 years, the PP-NRS will be completed by the caregiver. For subjects ages \geq 12 years, the PP-NRS will be completed by the subject.

An example of the PP-NRS is provided in [Appendix 13](#).

6.3.3 Optional Clinical Photography

Clinical photography may be performed in a subgroup of subjects at selected study sites. Informed consent/assent and photographic release will be required. The photographs may not be referred to by the Investigator at any subsequent study visit for the purposes of grading.

Photographs will be taken of a representative area of the subject's disease area at the time points specified in the Schedule of Assessments ([Table 1](#)). Photographs of the selected skin area will be taken in a standardized fashion (i.e., same camera, angle, background, distance).

6.4 Treatment of Study Drug Overdose

For this study, accidental or intentional oral ingestion of drug product will be considered an overdose. Ingestion of a 30-gram tube of tapinarof cream, 1% would result in an oral dose of 300 mg.

The Sponsor does not recommend specific treatment for an overdose; however, in the event of an overdose, the Investigator (or treating physician) should do the following:

- Contact Medical Monitor to discuss the event
- Closely monitor the subject for AEs/SAEs and laboratory abnormalities
- Provide general symptomatic treatment as necessary
- Document the quantity of the excess dose as well as the duration of the overdosing.

Decisions regarding dose interruptions or modifications following an overdose will be made by the Investigator in consultation with the Medical Monitor based on the clinical evaluation of the subject.

6.5 Virtual Assessments

In the event that a subject cannot attend their regularly scheduled study visits in person due to a COVID-19-like situation necessitating a limit on in-person contact, the Investigator may perform safety and efficacy assessments by phone or video. Source documentation should note if the visit was performed by phone or by video. The Investigator may use the technology platform that is currently available to them. Suggested platforms include Apple FaceTime, Zoom for Healthcare, Facebook Messenger video chat, Microsoft Teams, Google Hangouts video, and Skype. Additional details of the visit should be included in source documentation, as detailed in the Study Reference Manual.

If the subject can only be contacted by phone, the following should be assessed or performed:

- AEs
- Concomitant Medications
- Reminder to complete diary
- Instruction not to discard empty tubes of study drug

If the subject has video capabilities, the following items should be assessed or performed:

- AEs
- Concomitant Medications
- vIGA-AD™ assessment (excluding subject's scalp)
- %BSA assessment (excluding subject's scalp)
- EASI (excluding subject's scalp)
- [REDACTED]
- [REDACTED]
- Application of study drug by the subject or caregiver, if applicable
- Completion of the PP-NRS (the subject or caregiver [as applicable] can verbally indicate the answer which the study coordinator will document in the source document).
- Reminder to complete diary
- Instruction not to discard empty tubes of study drug

The reason that assessments cannot be completed during a virtual assessment (i.e., labs, vital signs, physical exams, etc.) must be noted (e.g., COVID-19) and the missed assessments will be recorded as protocol deviations.

7 Timing of Procedures and Assessments

This section lists the procedures and assessment to be performed at scheduled time points during the study as outlined in the Schedule of Assessments (Table 1). Information on study procedures and assessments is provided in Section 6.

- Any change in timing or any addition of a time point(s) for any planned study assessment must be documented in a “Note to File,” which is approved by the relevant Sponsor study team member and then archived in the study Sponsor and site study files; this will NOT constitute a protocol amendment.
- The IRB/IEC will be informed of any safety issues that require alteration of the safety monitoring or amendment of the ICF.

7.1 Visit 0; Screening Period for Direct-Enrolling Subjects (Day -30 to Day -1)

After the subject has signed the consent/assent form, potential study subjects will undergo Screening procedures and assessments to confirm eligibility to participate in the study. Screening assessments will include the following:

- Demography recording
- Fitzpatrick skin type
- Medical history recording
- Brief physical examination (including height and weight, body mass index will be calculated in the CRF)
- Vital signs measurements
- Serum pregnancy test (women of child-bearing potential [WOCBP])
- Blood sample collection for clinical laboratory tests (serum chemistry, hematology, diagnostic tests)
- Urinalysis
- vIGA-AD™ score (excluding subject’s scalp)
- %BSA affected calculation (excluding subject’s scalp)
- EASI (excluding subject’s scalp)
- AE recording (from the time the ICF is signed)
- Concomitant medication recording (including all medications administered up to 30 days prior to screening, and all systemic [oral and injectable] medications used by the subject for the treatment of AD prior to 30 days before Screening)

7.2 Visit 1; Baseline (Day 1)

7.2.1 Baseline Visit for Subjects Rolling Over from DMVT-505-3101 and DMVT-505-3102

On Day 1, subjects from the parent studies DMVT-505-3101 or DMVT-505-3102 who were considered eligible for this study will sign the ICF and be reassessed to confirm eligibility to participate in this study. All subjects who continue to meet study eligibility criteria will be enrolled. Subjects entering with a vIGA-AD™ ≥ 1 will receive treatment with tapinarof cream, 1% until they achieve a vIGA-AD™ score of 0, at which time treatment will be discontinued and subjects monitored for maintenance of the remittive effect. If/when

disease worsening occurs, as evidenced by a vIGA-AD™ ≥ 2 , treatment will then be re-initiated and continued until a vIGA-AD™ of 0 is observed. Subjects entering with a vIGA-AD™ of 0 will have treatment discontinued beginning at the Baseline visit and will be monitored for maintenance of the remittive effect.

The following procedures and assessments will be performed at the Baseline visit:

- Demographics and Fitzpatrick skin type (carried over from parent study)
- Medical history (carried over from parent study)
- Brief physical exam (last assessment from parent study)
- Vital signs measurements (last assessment from parent study)
- Urine pregnancy test (WOCBP; last assessment from parent study)
- Blood sample collection for clinical laboratory tests (serum chemistry and hematology; last assessment from parent study)
- Urinalysis (last assessment from parent study)
- vIGA-AD™ score (excluding subject's scalp; last assessment from parent study)
- %BSA affected calculation (excluding subject's scalp; last assessment from parent study)
- EASI (excluding subject's scalp; last assessment from parent study)
- [REDACTED]
- [REDACTED]
- [REDACTED]
- PP-NRS (last assessment from parent study)
- [REDACTED]
- [REDACTED]
- [REDACTED]
- Photography of a representative area of the subject's disease area (at a subset of study sites only; last photograph from parent study)
- AE recording (ongoing from parent study at the time the ICF is signed in this study)
- Concomitant medication recording (ongoing from parent study at the time the ICF is signed in this study)
- Dispense diary (subjects or their caregivers will be instructed in how and when to complete diary)
- Dispense study drug, if applicable
- Instruction on how to apply study drug, if applicable
- Study drug application under supervision, if applicable

7.2.2 Baseline Visit for Subjects Rolling Over from DMVT-505-2104

On Day 1, subjects from the parent studies DMVT-505-2104 who were considered eligible for this study will sign the ICF and be reassessed to confirm eligibility to participate in this study. All subjects who continue to meet study eligibility criteria will be enrolled. Subjects entering with a vIGA-AD™ ≥ 1 will receive treatment with tapinarof cream, 1% until they achieve a vIGA-AD™ score of 0, at which time treatment will be discontinued and subjects monitored for maintenance of the remittive effect. If/when disease worsening

occurs, as evidenced by a vIGA-AD™ ≥ 2 , treatment will then be re-initiated and continued until a vIGA-AD™ of 0 is observed. Subjects entering with a vIGA-AD™ of 0 will have treatment discontinued beginning at the Baseline visit and will be monitored for maintenance of the remittive effect.

The following procedures and assessments will be performed at the Baseline visit:

- Demographics and Fitzpatrick skin type (carried over from parent study)
- Medical history (carried over from parent study)
- Brief physical exam (last assessment from parent study)
- Vital signs measurements (last assessment from parent study)
- Urine pregnancy test (WOCBP; last assessment from parent study)
- Blood sample collection for clinical laboratory tests (serum chemistry and hematology; last assessment from parent study)
- Urinalysis (last assessment from parent study)
- vIGA-AD™ score (excluding subject's scalp; last assessment from parent study)
- %BSA affected calculation (excluding subject's scalp; last assessment from parent study)
- EASI (excluding subject's scalp; last assessment from parent study)
- [REDACTED]
- [REDACTED]
- [REDACTED]
- PP-NRS (last assessment from parent study)
- [REDACTED]
- [REDACTED]
- [REDACTED]
- AE recording (ongoing from parent study at the time the ICF is signed in this study)
- Concomitant medication recording (ongoing from parent study at the time the ICF is signed in this study)
- Dispense diary (subjects or their caregivers will be instructed in how and when to complete diary)
- Dispense study drug, if applicable
- Instruction on how to apply study drug, if applicable
- Study drug application under supervision, if applicable

7.2.3 Baseline Visit for Subjects Enrolling Directly into DMVT-505-3103

On Day 1, subjects will be reassessed to confirm continued eligibility to participate in the study. All subjects who continue to meet study eligibility criteria will be randomized to treatment.

The following additional procedures and assessments will be performed at the Baseline Visit:

- Changes to medical history will be recorded
- Brief physical examination
- Vital signs measurement
- Urine pregnancy test (WOCBP)

- Blood sample collection for clinical laboratory tests (serum chemistry and hematology)
NOTE: Blood sample collection for clinical laboratory tests is not required at the Baseline Visit if it has been \leq 14 days since samples were collected at Screening and the results of those clinical laboratory tests were within the normal range.
- Urinalysis
NOTE: Urine sample collection for urinalysis is not required at the Baseline Visit if it has been \leq 14 days since samples were collected at Screening and the results of those analyses were within the normal range.
- vIGA-AD™ score (excluding subject's scalp)
- %BSA affected calculation (excluding subject's scalp)
- EASI (excluding subject's scalp)
- [REDACTED]
- [REDACTED]
- [REDACTED]
- PP-NRS (by subject or caregiver)
- [REDACTED]
- [REDACTED]
- [REDACTED]
- Photography of a representative area of the subject's disease area (at a subset of study sites only)
- AE recording
- Concomitant medication recording
- Dispense diary (subjects or their caregivers will be instructed on how and when to complete diary)
- Dispense study drug
- Instruction on how to apply study drug
- Study drug application under supervision

7.3 Visits 2 to 13; Treatment Period

Subjects will return to the study site at least every 4 weeks (\pm 3 days) during the 48-week monitoring period. The following assessments will be performed:

- Brief physical exam; Weeks 12, 24, 36 and 48 only
- Vital signs measurements
- Urine pregnancy test (WOCBP)
- Blood sample collection for clinical laboratory tests (serum chemistry and hematology); Weeks 12, 24, 36 and 48 only
- Urinalysis; Week 48 only
- vIGA-AD™ score (excluding subject's scalp)
- %BSA affected calculation (excluding subject's scalp)
- EASI (excluding subject's scalp)

7.4 Phone Contact at Week 2 (Day 15 ± 3 Days)

Subjects or their caregivers will be contacted by phone at Week 2 to review study drug application instructions, if applicable, and to record AEs and concomitant medication use. Subjects or their caregivers should be reminded to complete their daily diary and bring it with them to the next clinic visit.

7.5 Follow-Up Visit 14; Week 49 (Day 344 ±3 Days)

Subjects will return to the study site 1 week (± 3 days) after last treatment to complete follow-up assessments as follows:

- Brief physical examination
- Vital signs measurement
- Blood sample collection for clinical laboratory tests (serum chemistry and hematology)
- Urinalysis
- vIGA-AD™ score (excluding subject's scalp)
- %BSA affected calculation (excluding subject's scalp)
- EASI (excluding subject's scalp)
- [REDACTED]
- [REDACTED]
- PP-NRS (by subject or caregiver)
- [REDACTED]
- [REDACTED]

- AE recording
- Concomitant medication recording

7.6 Unscheduled Visits

Unscheduled visits may occur, as needed. For subjects who experience suspected disease worsening (vIGA-AD™ ≥ 2) between scheduled study visits may contact the study site to arrange an unscheduled visit (see Section 5.1.5.2). The following assessments may be performed:

- Brief physical exam
- Vital signs measurements
- Urine pregnancy test (WOCBP)
- Blood sample collection for clinical laboratory tests (serum chemistry and hematology)
- Urinalysis
- vIGA-AD™ score (excluding subject's scalp)
- %BSA affected calculation (excluding subject's scalp)
- EASI (excluding subject's scalp)
- [REDACTED]
- PP-NRS (by subject or caregiver)
- [REDACTED]
- AE recording
- Concomitant medication recording
- Collect and review subject diaries for treatment compliance, if applicable
- Dispense subject diaries, if applicable
- Collect and dispense study drug, if applicable
- Review instructions on how to apply study drug, if applicable
- Study drug application under supervision, if applicable

If disease worsening is confirmed, a new treatment course will be initiated.

7.7 Early Termination Visit

Subjects who withdraw early from the study will be asked to return to the study site to complete early termination assessments as follows:

- Brief physical examination
- Vital signs measurement
- Urine pregnancy test (WOCBP)
- Blood sample collection for clinical laboratory tests (serum chemistry and hematology)
- Urinalysis
- vIGA-AD™ score (excluding subject's scalp)
- %BSA affected calculation (excluding subject's scalp)
- EASI (excluding subject's scalp)

- [REDACTED]
- [REDACTED]
- [REDACTED]
- PP-NRS (by subject or caregiver)
- [REDACTED]
- [REDACTED]
- [REDACTED]
- [REDACTED]
- [REDACTED]
- AE recording
- Concomitant medication recording
- Collect subject diaries
- Review subject diaries for treatment compliance
- Collect study drug

7.8 End of Study

The end of study is defined as when the last active subject has completed the Week 49 Follow-up Visit one week after the end of treatment.

8 Safety Monitoring and Reporting

8.1 Adverse Events, Serious Adverse Events, and Adverse Events of Special Interest

The Investigator or site staff is responsible for detecting, documenting, and reporting events that meet the definition of an AE, SAE, or adverse event of special interest (AESI). At each visit/contact, subjects should be questioned in a general way so as not to introduce bias in detecting AEs and/or SAEs. Open-ended and non-leading verbal questioning of the subject is the preferred method to inquire about AE occurrence.

Investigators are not obligated to actively seek AEs or SAEs in former study subjects. However, if the Investigator learns of any SAE, including a death, at any time after a subject has been discharged from the study, and he/she considers the event reasonably related to the study drug or study participation, the Investigator should promptly notify the Sponsor.

A narrative will be written and included in the Clinical Study Report for all SAEs and AESIs, and for all AEs that lead to study discontinuation

8.1.1 Definition of Adverse Events

An AE is any untoward medical occurrence in a subject temporally associated with the use of a medicinal product, whether considered causally related or not related to the medicinal product.

An AE can therefore be any unfavorable and unintended sign (including an abnormal laboratory finding), symptom, or disease (new or exacerbated) temporally associated with the use of a medicinal product.

Events meeting the definition of an AE include:

- Any abnormal laboratory test results (hematology, clinical chemistry) or other safety assessments (e.g., vital signs measurements), including those that worsen from Baseline, and felt to be clinically significant in the medical and scientific judgment of the Investigator
- Exacerbation of a chronic or intermittent pre-existing condition (e.g., plaque psoriasis) including either an increase in frequency and/or intensity of the condition
- For skin-related AEs, it should be noted whether or not the event is in the area of active application of study drug, and/or if spreading beyond the application site.
- New conditions detected or diagnosed after study drug administration even though it may have been present prior to the start of the study
- Signs, symptoms, or the clinical sequelae of a suspected interaction
- Signs, symptoms, or the clinical sequelae of a suspected overdose of either study drug or a concomitant medication (overdose per se will not be reported as an AE/SAE)
- "Lack of efficacy" or "failure of expected pharmacological action" per se will not be reported as an AE or SAE. Such instances will be captured in the efficacy assessments. However, the signs, symptoms, and/or clinical sequelae resulting from lack of efficacy will be reported as AE or SAE if they fulfill the definition of an AE or SAE.

Events that **do not** meet the definition of an AE include:

- Any clinically significant abnormal laboratory findings or other abnormal safety assessments that are associated with the underlying disease, unless judged by the Investigator to be more severe than expected for the subject's condition

- The disease/disorder being studied or expected progression, signs, or symptoms of the disease/disorder being studied, unless more severe than expected for the subject's condition
- Medical or surgical procedure (e.g., endoscopy, appendectomy); the condition that leads to the procedure is an AE
- Situations where an untoward medical occurrence did not occur (social and/or convenience admission to a hospital)
- Anticipated day-to-day fluctuations of pre-existing disease(s) or condition(s) present or detected at the start of the study that do not worsen

8.1.2 Definition of Serious Adverse Event

If an event is not an AE per Section 8.1.1, then it cannot be an SAE even if serious conditions are met (e.g., hospitalization for signs/symptoms of the disease under study, death due to progression of disease, etc.).

An SAE is any untoward medical occurrence that, at any dose:

- Results in death
- Is life-threatening
 - The term “life threatening” refers to an event in which the subject was at risk of death at the time of the event. It does not refer to an event, which hypothetically might have caused death, if it were more severe.
- Requires hospitalization or prolongation of existing hospitalization
 - In general, signifies that the subject has been detained (usually involving at least an overnight stay) at the hospital or emergency ward for observation and/or treatment that would not have been appropriate in the physician's office or outpatient setting. Complications that occur during hospitalization are AEs. If a complication prolongs hospitalization or fulfills any other serious criteria, the event is serious. When in doubt as to whether “hospitalization” occurred or was necessary, the AE should be considered serious.
 - Hospitalization for elective treatment of a pre-existing condition that did not worsen from Baseline is not considered an AE.
- Results in disability/incapacity: a substantial disruption of a person's ability to conduct normal life functions.
 - This definition is not intended to include experiences of relatively minor medical significance such as uncomplicated headache, nausea, vomiting, diarrhea, influenza, and accidental trauma (e.g., sprained ankle) which may interfere or prevent everyday life functions but do not constitute a substantial disruption.
- Results in a congenital anomaly/birth defect

Medical or scientific judgment should be exercised in deciding whether reporting is appropriate in other situations, such as important medical events that may not be immediately life-threatening or result in death or hospitalization but may jeopardize the subject or may require medical or surgical intervention to prevent one of the other outcomes listed in the above definition. These should also be considered serious. Examples of such events are invasive or malignant cancers, intensive treatment in an emergency room or at home for

allergic bronchospasm, blood dyscrasias, or convulsions that do not result in hospitalization, or development of drug dependency or drug abuse.

8.1.3 Adverse Events of Special Interest

In prior clinical studies, contact dermatitis, folliculitis, and headache have been identified as AEs of particular clinical importance and will be reported as AESIs in this study whether or not the AE is considered related to study drug.

In each case study drug may be continued or discontinued, based on Investigator judgment, and may be restarted when the event resolves. In addition, the following information must be collected for each of these AESIs:

Contact Dermatitis

Contact dermatitis: the study site should collect location, duration, size, associated symptoms (itching, burning, pain), severity (mild, moderate, severe), time to onset, and photograph the affected site (if possible). If the subject or caregiver contacts the study site to report significant skin irritation at or near the site of study drug application between study visits, the subject should be brought in for an unscheduled visit, if possible.

Headache

The study site should collect duration, severity (mild, moderate, severe), time to onset, and location (e.g., frontal, temporal, occipital, diffuse).

Follicular Event

The study site should collect the location, duration, size, associated signs and symptoms (itching, burning, pain, erythema), severity (mild, moderate, severe), describe morphology [scale (keratotic/cornified) or no scale (non-keratotic/non-cornified)], time to onset, and photograph the affected site (if possible). Additional information regarding management of folliculitis is provided in Section 8.2.1.2.4.

In particular, the term ‘folliculitis’ may not correctly describe the morphology of the observed local follicular events as these appear to be more consistent with a keratoses pilaris-like follicular based papule. Tapinarof upregulates components of the stratum corneum, including involucrin, hornerin, and filaggrin and increased cornification at, and subsequent mechanical occlusion of, the follicular ostia has been suggested to be a potentially on target mechanism by which these lesions may develop in some individuals treated with tapinarof cream. Additional morphologic description will help to more fully and appropriately characterize these follicular events.

Possible descriptors include, but are not limited to:

- Folliculitis
 - Non-inflammatory
 - Inflammatory
- Milia
 - Non-inflammatory
 - Inflammatory
- Keratosis pilaris
 - Non-inflammatory

- Inflammatory

Additional AESIs may be identified during the evaluation of safety data for the Clinical Study Report.

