4.5.1 Reasons for Withdrawal from the Study

Study drug will be discontinued and the subject withdrawn from the study for any of the following reasons:

- Subject has an AE that is considered to be related to study drug or procedures AND is severe enough to warrant treatment discontinuation, as determined by the Investigator (Section 8.1).
- Pregnancy
- Any Grade 3 or 4 AE, based on Cancer Institute Common Terminology Criteria for Adverse Events (CTCAE) criteria, considered causally related to study drug (Section 8.2.2)

Study drug may be discontinued and the subject withdrawn from the study for any of the following reasons:

- Subject requires concurrent prohibited medication during the study (Section 5.6.2). Nonmedicated emollients that do not contain salicylic acid may be used on nonlesional skin but the subject (or caregiver) should wait at least 30 minutes after applying study drug before applying nonmedicated emollients; emollients should not be applied to lesional skin during treatment. The same emollient should be used throughout the subject's participation in the study.

NOTE: If, in the opinion of the Investigator and the study Medical Monitor, such medication will not interfere with the conduct or interpretation of the study or compromise the safety of the subject, then the subject may continue to receive study drug.

- Subject noncompliance
- Investigator noncompliance
- Discontinuation of the study at the request of the Sponsor, regulatory agency, or an Institutional Review Board (IRB)/Independent Ethics Committee (IEC).

If a subject meets a withdrawal criterion during treatment, an Early Termination visit will be required (Section 7.7).

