4.5.2 Withdrawal Procedures

The primary reason for the discontinuation of study drug and/or withdrawal from study must be recorded in the source document and on the case report form (CRF). If a subject is prematurely discontinued from study drug, the Investigator must make every effort to perform an Early Termination Visit (Section 7.7) and document the primary reason for withdrawal.

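### Protocol 8.1.3 lets the Investigator continue or restart study drug for any AESI, which conflicts with the required stop and withdrawal for a related Grade 3 event

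*Protocol*

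**What the plan says.** Protocol Section 8.1.3 names contact dermatitis, folliculitis and headache as adverse events of special interest (AESIs). These events "will be reported as AESIs in this study whether or not the AE is considered related to study drug". On drug handling it says: "In each case study drug may be continued or discontinued, based on Investigator judgment, and may be restarted when the event resolves". It then lists the data to record. For headache: "The study site should collect duration, severity (mild, moderate, severe), time to onset, and location". The same three severity levels appear for contact dermatitis and for follicular events. The only management section it points to is 8.2.1.2.4, on folliculitis.

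Section 4.5.1 has a mandatory list and a discretionary list. The mandatory one opens: "Study drug will be discontinued and the subject withdrawn from the study for any of the following reasons". It includes: "Any Grade 3 or 4 AE, based on Cancer Institute Common Terminology Criteria for Adverse Events (CTCAE) criteria, considered causally related to study drug". It closes: "If a subject meets a withdrawal criterion during treatment, an Early Termination visit will be required".

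Section 8.2.1.2 sets the action by grade:

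- **Grade 1 or 2 (8.2.1.2.1):** the Investigator may keep the subject on drug.
- **Grade 3 (8.2.1.2.2):** drug should be discontinued if the event is related. Otherwise dosing may go on only with compelling evidence that the drug was not the cause, and after discussion with the Medical Monitor.
- **Grade 4 (8.2.1.2.3):** drug should be stopped permanently, with no condition on causality.

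None of these sections exempts AESIs.

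**The concern.** Two instructions apply to the same event and give different answers. Take a subject with a severe contact dermatitis that the Investigator judges related to the cream. Under 8.1.3 the Investigator may carry on dosing, or pause and restart. Under 4.5.1 dosing must end and the subject leaves the study. A subject who has been withdrawn cannot be restarted.

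The question is whether to keep dosing after a severe drug-related reaction, in a study that enrolls children from age 2, for events that the protocol itself singles out as clinically important. A site that relies on 8.1.3 could expose a subject to further harm and would depart from 4.5.1. With up to about 135 sites, different sites could also handle the same event differently.

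**Working it through.** No arithmetic applies. The check sets the rules side by side by grade and causality, then looks for text that ranks them.

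**Scope of 8.1.3.** The drug-handling sentence applies to each of the three event types. AESIs include related and unrelated events, and severe is a recorded level for all three. Table 5 in Section 8.2.1.1 equates severe with Grade 3 for terms that CTCAE does not specify. For terms that CTCAE does specify, I assume that severe also means Grade 3. The sentence therefore cannot be read as limited to mild or moderate events.

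**Comparison for an AESI.**

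| Grade and causality | 8.1.3 | Other sections | Result |
|---|---|---|---|
| 1 or 2, related or not | Investigator decides | 8.2.1.2.1: Investigator decides | Consistent |
| 3, unrelated | Investigator decides | 8.2.1.2.2: continue only with compelling evidence and Medical Monitor discussion | 8.1.3 omits a step |
| 3, related | Continue or restart allowed | 4.5.1: stop and withdraw; 8.2.1.2.2: discontinue | Conflict |
| 4, related | Continue or restart allowed | 4.5.1: stop and withdraw; 8.2.1.2.3: permanent stop | Conflict in principle |
| 4, unrelated | Continue or restart allowed | 8.2.1.2.3 only: permanent stop | Conflict in principle, resting on a "should"-type rule alone |

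**Strength of the related Grade 3 row.** Both 4.5.1 and 8.2.1.2.2 conflict with continuing the drug. On restarting, the conflict rests on 4.5.1. Section 8.2.1.2.2 omits the word permanent from its discontinuation rule and then speaks of Grade 3 events that need permanent discontinuation, so it can be read as leaving room for others that do not.

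**Is there a ranking?** No text makes 8.1.3 subject to 4.5.1 or to 8.2.1.2. Its only management cross-reference is to 8.2.1.2.4, which allows temporary interruption at folliculitis sites and sets no grade limit. The Grade 3 or 4 bullet in 4.5.1 refers to 8.2.2, which concerns causality. A reader could take the general stopping rules as overriding, or take the AESI sentence as a specific exception.

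**How many subjects?** The documents give no AESI rate by grade and causality, so no count can be computed. Section 8.2.1.2.4 says most folliculitis is mild or moderate, which points to a small number.

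**The case against.** The best defense is that 8.1.3 only permits and 4.5.1 commands. Stopping the drug satisfies every section. The opening of Section 6 bars waivers except for immediate safety concerns. Section 8.1.3 is mainly a list of events and data to collect, whereas 8.2.1.2 is the toxicity management section. On that view a sensible site reads the discretion as operating inside the stopping rules, and all that is missing is a subject-to clause. Section 8.2.1.2.5 also asks that the Medical Monitor be told of severe signs or symptoms that put the subject at risk.

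Much of this stands. A site can comply with everything, and the defect is one of drafting. But a permission that breaches a mandatory rule when it is used is more than missing detail, and the protocol does not state the sensible reading. The Medical Monitor notice depends on the Investigator's judgment and does not itself stop dosing.

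Three stronger readings are tempting and are not supported:

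- **A conflict for related Grade 1 or 2 events.** A reader might argue that pausing drug triggers the withdrawal criterion for an event "considered to be related to study drug or procedures AND is severe enough to warrant treatment discontinuation", and with it the rule in 4.5.2: "If a subject is prematurely discontinued from study drug, the Investigator must make every effort to perform an Early Termination Visit". But that criterion depends on the Investigator's own determination. An Investigator who pauses drug and intends to resume has not made it. Sections 8.2.1.2.1 and 8.2.1.2.4 allow discretion and interruption.
- **A serious Grade 4 problem.** Section 8.1.3 lists severity only from mild to severe, and nothing suggests that it has life-threatening events of these three kinds in view. Section 4.5.1 does not list unrelated Grade 4 events at all.
- **A threat to the analysis.** The study is descriptive, and SAP Section 13.2 already reports grade, causality and action taken for AESIs.

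**Conclusion.** The conflict is real and narrow. Read literally, 8.1.3 permits dosing after a related Grade 3 contact dermatitis, folliculitis or headache, where 4.5.1 requires the drug to stop and the subject to leave. For an unrelated Grade 3 AESI it does not prescribe an opposite action but drops a safeguard.

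This is a matter of subject safety and avoidable protocol deviations, likely to touch few subjects. The conclusion assumes that a severe AESI is graded 3, and that no separate site instruction outside these two documents already settles the order of the rules. It is worth correcting because the remedy is small and the event concerned is a severe drug-related reaction.

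**What to change.** Replace the drug-handling sentence in 8.1.3 with text to this effect:

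> Subject to Sections 4.5.1 and 8.2.1.2, for a Grade 1 or 2 AESI the Investigator may continue study drug or interrupt it temporarily, and may resume it once the event has resolved. Grade 3 and 4 AESIs are managed under Sections 4.5.1, 8.2.1.2.2 and 8.2.1.2.3.

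Saying interrupt rather than discontinue keeps a pause apart from the discontinuation that leads to an Early Termination visit. It also matches SAP Section 9.1, which counts permanent withdrawal and interruption as different outcomes.

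This edit does not align the stricter sections with each other. Section 4.5.1 requires withdrawal for a related Grade 3 event while 8.2.1.2.2 only encourages withdrawal evaluations, and 4.5.1 is silent on unrelated Grade 4 events. Both could be tidied in the same amendment, but the fix does not depend on it.

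The cost is a short protocol amendment. Sections 11.1.2 and 11.2.1 require ethics committee approval and regulatory submission before the change takes effect, so a notice to sites is not enough. The note-to-file route in Section 7 covers only the timing or addition of assessments. The change can be bundled with another amendment. It needs no new data, visits or analyses, and no SAP change.
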